# 11.2 Fasting Blood Draw

A fasting blood sample will be taken at Screening Visit 1 to assess inclusion criteria and overall health (HbA1c, Chem15 including ALT, creatinine, lipid panel and glucose), as well as during Visit 3 and Visit 6 to measure insulin, glucose, and free fatty acids (FFA). HbA1c and measures of Chem15 panel will also be obtained at Visit 6. Fasting blood will also be archived at Visit 3 and Visit 6.

### 11.3 Overnight oximetry

Pulse oximeters (Nonin WristOX2) will be provided to the participants during Screening Visit 1 to determine risk for sleep apnea. Participants will be asked to use the oximeter for one night of sleep. Determination of nocturnal oxygen desaturations to objectively asses risk for sleep apnea will be important to reduce screen failures. Only participants with oxygen desaturation index (ODI) >15 events/h of sleep will be asked to participate in the overnight sleep study. Participants may be asked to repeat oximetry if incomplete data are obtained.

# 11.4 Overnight sleep study (Polysomnography, PSG)

Overnight video PSG will be performed in individuals with ODI >15 events/h at PI's lab at Screening Visit 2. PSG will include electroencephalography, electrooculography, electromyography, electrocardiography, pulse oximetry, nasal pressure transducer, oronasal thermocouple, calibrated respiratory inductance plethysmography. Sleep staging and events will be scored by registered PSG technologists according to AASM established criteria and report will be finalized by a Sleep Board Certified Physician ([name]). PAP prescription will be generated for the eligible participants and provided to ApneaMed to procure appropriate PAP device.

# 11.5 Body Composition (by Dual-Energy X-ray Absorptiometry)

Dual-energy X-ray absorptiometry (DXA) scans will be performed at the Imaging Facility of PBRC at Visit 3 and Visit 6. Total adiposity and regional fat mass will be assessed with DXA using a whole-body scanner (Lunar iDXA; General Electric, Milwaukee, WI). The DXA protocol requires that participant lie on a table wearing a hospital gown and with no metal objects on them while both legs will be placed together using two Velcro straps. The scanner emitting low energy X-rays and a detector passes along the body. The scan takes ~10 minutes and the radiation dose is less than 1 mrem, equal to about 12-h of background radiation. The scans will be analyzed with the latest software. The software version is enCORE 13.6. We will run quality control scans on a daily basis, and GE has indicated that accuracy of the data is confirmed with these daily QC scans. If needed,

a pregnancy test will be given before DXA scans to confirm absence of pregnancy. Fat mass will be calculated by taking the metabolic weight (i.e., total body weight minus gown weight) multiplied by the regional percent body fat given by the DXA.

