# **10. STUDY VISITS**

# 10.1 Visit 3 (Baseline)

Participants will arrive to PBRC for an early morning fasting visit. Body weight will be measured along with measurement of waist, hip, arm and neck circumference. Blood sample will be drawn, questionnaires will be administered, and if needed, urine pregnancy test will be conducted. Participants will be given a standard glucose drink (75g glucose) to consume while timed blood samples will be collected every 30 min for 2 hours to measure glucose, insulin and free fatty acids (FFA). An abdominal adipose tissue biopsy and a skeletal muscle biopsy will be performed. Participants will also undergo whole-body DXA to determine body composition. At the end of this visit, participants will be provided a monitor to measure 24-h ambulatory blood

pressure and study drug will be dispensed with appropriate dose and safety instructions. Lunch will be provided prior to discharging the participants.

Following this visit, we will provide the study participants with PAP therapy through standard on-line resources (ApneaMD). PAP devices will be given to the participants at PBRC. PI will obtain equipment serial number to monitor adherence. For the first 4-weeks, study personal will monitor PAP compliance weekly (on-line data). Thereafter, we will monitor compliance on a monthly basis. Appropriate PAP use will be encouraged via additional consults and/or mask replacement as needed.

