### 14.4.2 Statistical Analyses

The primary outcome is insulin sensitivity via Matsuda Index. We will use mixed effect linear models, accounting for correlation over time and treatment to assess outcome difference in metformin and placebo treated groups. Primary analysis will be conducted on all study participants who have taken one dose of the study drug and used CPAP for at least one night. Sensitivity analyses will be conducted on per-protocol sample of subjects adherent to the study interventions. Publications will acknowledge the limitation of small sample and any other weaknesses.

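### Section 11.5's only fat-mass formula multiplies whole-body weight by a regional fat percentage; on its ordinary reading this overstates regional fat and does not give total fat

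*Combined protocol and SAP*

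**What the plan says.** Section 11.5 sets out what DXA is to deliver: "Total adiposity and regional fat mass will be assessed with DXA using a whole-body scanner". These are two different quantities. The section then gives a single rule for fat mass: "metabolic weight (i.e., total body weight minus gown weight) multiplied by the regional percent body fat given by the DXA".

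The weight term is explicitly whole-body weight less the gown. The percentage is explicitly regional. The section does not say which region is meant, whether the percentage is of the region's mass or of the whole body's mass, or whether the product is total or regional fat. It contains no region-mass term and no separate rule for total fat, and no other section supplies either.

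The scans "will be performed at the Imaging Facility of PBRC at Visit 3 and Visit 6", so the rule would be used at baseline and at month 3. Section 10.1 gives the purpose: "Participants will also undergo whole-body DXA to determine body composition". Section 14.4.2 does not mention fat mass; there, "The primary outcome is insulin sensitivity via Matsuda Index".

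**The concern.** A percentage has to be multiplied by the mass it is a percentage of. Whole-body weight goes with whole-body percent fat, and a region's percent fat goes with that region's mass. Section 11.5 crosses the two. An analyst who follows the sentence literally would report regional fat masses that are too large in every region and that can add up to more than the participant weighs. A colleague who took the percentage to be the whole-body figure would report something quite different from the same scan.

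What is at stake is the body-composition description at both visits and the change between them. Section 14.4.1 says the pilot is meant to establish effect sizes for a later grant application, so mis-scaled fat masses could be carried forward if body composition is used there.

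**Working it through.** The plan states no numerical fat mass, so there is no figure to reproduce. The check is algebra, followed by an illustration.

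**Notation.** W is metabolic weight, w the mass of a region, f the fat in that region and F total fat. The Section 11.5 rule returns W × p, where p is the regional percentage.

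**Three possible meanings of p**

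- (a) Percent fat of the region's own mass, p = f/w, the ordinary meaning. The rule returns W × f/w = f × (W/w). Regional fat is overstated by exactly W/w, which exceeds 1 for any part of the body.
- (b) The whole-body value, p = F/W. The rule returns F. Total fat is correct, and regional fat has no formula.
- (c) Region fat as a percentage of whole-body mass, p = f/W. The rule returns f. Regional fat is correct, total fat has no explicit formula, and the unusual denominator is stated nowhere.

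**Size under (a).** The factor is 1 divided by the region's share of body mass. The shares are assumptions:

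| Assumed share of body mass | Overstatement |
|---|---|
| 60% | 1/0.60 = 1.67 |
| 50% | 1/0.50 = 2.0 |
| 33% | 1/0.33 = 3.03 |
| 12% | 1/0.12 = 8.33 |

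**Illustration under (a).** W = 100 kg. All shares and fat percentages are assumed.

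| Region | Mass (kg) | Percent fat | True fat (kg) | Rule gives (kg) |
|---|---|---|---|---|
| Trunk | 50 | 46 | 50 × 0.46 = 23.0 | 100 × 0.46 = 46 |
| Legs | 33 | 42 | 33 × 0.42 = 13.86 | 100 × 0.42 = 42 |
| Arms | 12 | 40 | 12 × 0.40 = 4.8 | 100 × 0.40 = 40 |
| Head | 5 | 25 | 5 × 0.25 = 1.25 | 100 × 0.25 = 25 |
| Sum | 100 | | 42.91 | 153 |

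The rule's four results sum to 153 kg of fat in a 100 kg person. Nor is any one of them total fat: against 42.91 kg they stand at 1.07 (trunk), 0.98 (legs), 0.93 (arms) and 0.58 (head). The rule would match total fat only if the region's percentage happened to equal the whole-body percentage.

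**Change from Visit 3 to Visit 6 under (a)**

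- Region's share of body weight stable: W/w is the same at both visits. Percent change is correct, and kilogram change is inflated by W/w.
- Weight lost only outside the trunk (assumed 110 to 107 kg, trunk 57 kg at 46% throughout): the rule goes from 110 × 0.46 = 50.6 to 107 × 0.46 = 49.2 kg, an apparent loss of 1.4 kg (2.7%). True trunk fat does not change.
- Trunk loses more than its share (assumed W 100 to 97 kg, trunk 50 to 47.5 kg, trunk percent fat 46 to 45): the true change is 47.5 × 0.45 − 50 × 0.46 = −1.625 kg, or −7.1% of 23.0. The rule gives 97 × 0.45 − 100 × 0.46 = −2.35 kg, or −5.1% of 46. The kilogram loss is overstated and the relative loss understated.

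**The case against.** The best defence is that Section 11.5 never defines the region or the denominator. The sentence says fat mass, not regional fat mass, and multiplies by total body weight. That fits a correct formula for total fat with one misplaced word. Results summing to more than body weight would also be hard to overlook in practice. This stands in part: a reader might infer that the rule certainly gives neither total nor regional fat mass, and the documents do not support that certainty. But each rescuing reading still leaves one of the two promised quantities without an explicit formula and requires the sentence to be changed.

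A reader might also infer that a weight difference between arms would show up as a false loss of trunk fat on metformin, since Section 4.2 lists mild anorexia. This does not follow in general. Percent change is correct when the region's share of body weight is stable. A spurious loss needs weight to be lost disproportionately elsewhere, and the relative bias reverses when the region itself loses disproportionately. The documents give no expected weight difference between arms.

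Finally, DXA might be taken as the measure that explains any change in insulin sensitivity. The documents do not give it that role. Fat mass appears in neither the aims (Section 2) nor the statistical plan (Section 14.4), and Table 1 also schedules body weight and circumferences at Visits 3 and 6.

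**Conclusion.** The point holds as a faulty formula on its ordinary reading and an incomplete one on any other. If the percentage is of the region's own mass, regional fat is overstated by exactly body weight over region weight, and the result is not total fat. The direction and the factor follow from algebra. The range of about 1.7 to 8.3 times rests on assumed region shares of 60% to 12%, because the documents give none. Kilogram values are then wrong at both visits, and relative change is also distorted when the region's share of body weight shifts.

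The reach is limited. The Matsuda Index formula in Section 11.7 contains no fat mass, and the sample-size text in Section 14.4.1 does not use it. This is a body-composition measure outside the primary analysis. The sentence should be corrected, but it does not threaten the trial's main result.

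**What to change.** Replace the last sentence of Section 11.5 with:

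> Total fat mass = metabolic weight × whole-body percent fat from DXA. Regional fat mass = that region's mass × that region's percent fat, or the DXA-reported regional fat mass if the software reports it.

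Name the regions to be reported, and state that the same rule applies at Visit 3 and Visit 6.

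This is correct whichever meaning was intended. It costs a short text change and a check of which regional quantities the software exports, since the documents mention only a percentage. No added scan, visit or procedure is needed. Any fat masses already derived should be checked against the new rule and recalculated where they differ.

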### **11.6 Three-day Dietary Records**

Participants will be given instruction and a form to complete dietary record for 3 non-consecutive days which would include 2 weekdays and 1 weekend during Visit 3 and Visit 6. This would provide rough estimation of the participants' normal daily intake and any changes that may be mediated by PAP and/or metformin treatment.

# 11.7 Oral Glucose Tolerance Test

Glucose tolerance will be assessed using an oral 75 g oral glucose tolerance test (OGTT). Participants will be studied after an overnight fast. An intravenous line will be placed and one baseline sample will be drawn at -5 minutes. The participants will then consume a 75 g glucose beverage within 5 minutes. Blood samples will be collected at 30, 60, 90, and 120 to measure serum glucose, insulin and free fatty acid concentrations. Whole body insulin sensitivity will be calculated using Matsuda index (10,000/  $\sqrt{$ [fasting glucose X fasting insulin] X [mean OGTT glucose X mean OGTT insulin]) and other indices related to whole body glucose homeostasis. Adipose tissue insulin sensitivity will be calculated using ISI- FFA [2/(Insulin AUC X FFA AUC) +1].

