#### AIM 1: To determine the effects of metformin + PAP on whole body insulin sensitivity (IS).

Hypothesis: Addition of metformin to PAP therapy in OSA patients will enhance reduction in IR. Measures derived from oral glucose tolerance test including Matsuda index (whole body-IS) and ISI-FAA (AT-IS) will be used to longitudinally examine changes in IS to inform about metabolic risk reduction in OSA patients.

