#### 14.4.1 Sample Size Considerations

Although a formal power analysis was not feasible in this randomized, crossover pilot trial, we can expect significant improvements to be detectable with up to 18 completers for whole-body insulin sensitivity determined by Matsuda Index. Importantly, the proposed trial will be used to generate first-of-its-kind preliminary data for our investigative team to establish effect sizes and, therefore, develop power calculations as part of a future R01-level grant application.

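### Do the ambiguous bracket and missing units in the ISI-FFA formula of section 11.7 undermine the adipose insulin-sensitivity results?

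*Combined protocol and SAP*

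**What the plan says.** Aim 1 names two OGTT measures, the Matsuda index for the whole body and a second index for adipose tissue: "ISI-FAA (AT-IS) will be used to longitudinally examine changes in IS". Section 11.7 defines the second one, spelled ISI-FFA there, as "2/(Insulin AUC X FFA AUC) +1". The expression stands inside square brackets and is followed by a citation to reference 12.

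On sampling, section 11.7 states "one baseline sample will be drawn at -5 minutes" and then "Blood samples will be collected at 30, 60, 90, and 120 to measure serum glucose, insulin and free fatty acid concentrations". Section 10.1 agrees: "timed blood samples will be collected every 30 min for 2 hours to measure glucose, insulin and free fatty acids (FFA". Neither section gives concentration units, a time unit, a reference value, the choice between total and incremental AUC, or the integration rule.

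Section 14.4.2 makes the Matsuda index the primary outcome and sets the model: "We will use mixed effect linear models, accounting for correlation over time and treatment". Section 14.4.1 says the trial will be used "to establish effect sizes and, therefore, develop power calculations as part of a future R01-level grant application", and names only the Matsuda index when it discusses what may be detectable. Section 14.4 refers to a separate pre-specified analysis plan.

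**The concern.** By ordinary precedence the inner parenthesis closes before the 1 is added, so the index reads 1 + 2/(Insulin AUC x FFA AUC). Three things then look wrong.

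- With total AUCs the 1 is only a floor. In minute-based units every participant would score almost exactly 1.
- A pure number added to a quantity with units has no clear meaning unless the AUC product has first been made dimensionless, and no scaling is given.
- The printed form is not a linear transform of 2/(product + 1). The two readings can therefore give different estimates, standardised effects and p-values.

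At stake would be the reported level of the index, any percent change, comparison with other studies, and the adipose effect size carried into a later grant application. An undefined formula could also leave room to choose between forms after the data are seen.

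**Working it through.** The documents report no ISI-FFA value, so there is no figure to reproduce. All profiles and variances below are assumed.

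**1. Level of the index.** Trapezoid AUCs over 0, 30, 60, 90 and 120 minutes, insulin in uU/mL, FFA in mmol/L:

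| Profile | Insulin AUC | FFA AUC | Product P | 1 + 2/P, minutes | hours (P/3600) | nmol/L and hours (P x 0.006/3600) |
|---|---|---|---|---|---|---|
| Low | 3,840 | 23.40 | 89,856 | 1.0000223 | 1.080 | 14.35 |
| Mid | 9,210 | 36.45 | 335,705 | 1.0000060 | 1.021 | 4.57 |
| High | 16,125 | 54.90 | 885,263 | 1.0000023 | 1.008 | 2.36 |

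The last column assumes 1 uU/mL = 6 pmol/L. The level does depend on units, as the concern says.

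**2. The planned comparison.** Write Y = 1 + 2/P. A change of units replaces P by kP, so Y' = 1 + (Y - 1)/k. Every change from baseline is divided by k, and so is its standard deviation. The t statistic, the p-value and the standardised effect stay the same, and the untransformed linear model of section 14.4.2 behaves likewise. One simulated dataset (9 per arm, median product 210,000, log-SD 0.7, correlation 0.6, treated product x 0.6) gave t = 2.84, p = 0.0118 in minutes, in hours, and in nmol/L with hours. The treated arm's mean percent change was 0.002%, 8% and 186% respectively, but section 14.4.2 plans no percent-change analysis.

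**3. Where the bracket matters.** 20,000 simulated trials, 9 per arm (18 completers, section 14.4.1), t-test on change, log-SD 0.8, correlation 0.6, treated product halved:

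| Scale of the product | Power, 2/P + 1 | Power, 2/(P + 1) | Verdicts that differ |
|---|---|---|---|
| Minutes, median 210,000 | 39.5% | 39.5% | 0.0% |
| Hours, median 210,000/3600 = 58 | 39.5% | 42.0% | 2.5% to 2.7% across runs |
| Rescaled to median 1 | 40.5% | 47.4% | 22.0% |

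When P is large, P + 1 is nearly P and the two forms are almost linearly related. They part only when P is near or below 1. With log-SD 0.6 and correlation 0.5, the rescaled case gives 61.5% against 61.9%, with 17.4% of verdicts differing.

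**4. Cost of the bracketed form.** On unscaled AUCs its p-value moves with units. The dataset in step 2 gives 0.0118 in minutes, 0.0103 in hours, and 0.0210 in nmol/L with hours.

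**5. AUC rule.** FFA falls after glucose, so incremental FFA AUC is negative. In the mid profile it is 36.45 - 120 x 0.55 = -29.55. Incremental insulin AUC is 9,210 - 120 x 14 = 7,530. The hour-based index is then 1 + 2/(7,530 x -29.55/3600) = 0.968, below its own floor. Total AUC is the only sensible reading of the unqualified term. Starting the area at -5 rather than 0 minutes, on a second assumed profile, moves the product from 324,360 to 357,556 (ratio 1.10). The same rule would apply to both arms and both visits.

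**The case for a change.** The strongest case for a change is that correcting the bracket does not complete the definition. If the 1 belongs in the denominator, the result depends on scale, and no scale is given. In nmol/L and hours the median product is 210,000 x 0.006/3600 = 0.35, close to the region where the two forms disagree often. On the rescaled simulation the median standardised effects are 0.89 and 0.96. By 2(1.96 + 0.842)^2/d^2 these imply about 20 and 17 per arm in a later trial, and generating such effect sizes is a stated purpose of this one. A line or two written before unblinding would settle it.

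Two parts of this stand. The level of the index cannot be reproduced from this text alone, and two analysts using the bracketed form in different units could get different p-values.

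The rest does not carry a change. The scale dependence belongs to the bracketed form. The printed form does not have it. Neither the bracketed form nor a reference value can be derived from these documents, because the cited source is not part of them. Prescribing that form would bring in the dependence the objection warns about. Analysing the log of the product avoids the scale problem, but it replaces a cited index. Its gain over the printed form (48.8% against 40.5%, and 63.5% against 61.5%) comes from simulations that assume lognormal data, which favours the log.

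**Conclusion.** No change to the plan is needed. The bracket is most likely a clerical or extraction slip: the outer square bracket encloses the 1, and the Matsuda formula in the preceding sentence also has broken brackets. The ISI-FAA spelling in Aim 1 is a plain typing error. Units, the trapezoid rule and use of the -5 minute sample as the baseline point are details an analyst fills in as a matter of course, from the cited source or the separate analysis plan. The index can be recomputed from stored OGTT values at any time.

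The consequence is small. The primary Matsuda analysis is untouched, and Aim 2 measures adipose insulin action separately, ex vivo. Taken literally, the printed index gives a between-arm test and a standardised effect that do not depend on units. Against the bracketed alternative, the verdict differs in 0.0% of simulated trials with AUCs in minutes and about 2.5% in hours. The larger disagreement requires a product near or below 1, through rescaling or a particular choice of units.

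This rests on the assumed profiles, lognormal products and 9 per arm, and on an untransformed analysis as section 14.4.2 describes. It does not depend on knowing which bracket placement the cited source uses.

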# **11.8 Ambulatory Blood Pressure Monitoring**

Ambulatory 24-hour blood pressure (BP) and heart rate will be continuously collected via an Ambulatory BP Monitor (or ABPM) starting in the afternoons of Visit 3 and Visit 6. The system will be programmed to record blood pressure and heart rate every 30 minutes during the day and night. The blood pressure cuff will be placed on the *non-dominant* arm. Both written and oral instructions pertinent to the use of ABPM will be provided to all participants. Volunteers will be instructed to avoid caffeine, alcohol, moderate-to-vigorous exercise, and daytime naps during this period and asked to maintain an Activity Log (bedtimes, mealtime, physical activity, showering, etc.). Participants taking antihypertensive medications will be instructed to adhere to their prescribed dosing. The ABPM records key aspects of blood pressure including 24-hour, daytime and nighttime systolic BP, diastolic BP, mean BP, and heart rate. Participants may be asked to repeat the blood pressure monitoring if incomplete data are obtained.

# **11.9 Biopsies**

On the mornings of Visit 3 and Visit 6, skeletal muscle and adipose tissue biopsies will be performed in the PBRC Inpatient Unit on the *non-dominant* side of the body.

